3.12. Interim Analyses

No formal interim analysis is currently planned for this study; however, given the exploratory nature of the study, various data cuts may occur in support of business decision making or regulatory submission such as a New Drug Application. The timing of these data cuts and the number of patients included in each analysis will take into account specific requests from regulatory agencies and applicable regulatory guidance.

Additionally, various data cuts may occur once a pre-specified number of patients in each subgroup of RGDO have completed ~3 months of treatment with setmelanotide. The number of patients may depend on the prevalence of each subgroup of RGDO.

After enrollment of a subgroup of RGDO patients has been completed and all patients in that subgroup have completed the study, their data may be finalized, and an interim analysis of their final data may be performed.

4. STUDY ANALYSES

4.1. Patient Disposition

Patient disposition will be tabulated and include the number screened, the number enrolled, the number enrolled prior to amendment 9, the number enrolled post-amendment 9, the number treated, the number in each patient population for analysis, and the number who withdrew prior to completing the study and reason(s) for withdrawal.

A by-patient data listing of study completion information including the reason for premature study withdrawal, if applicable, will be presented. Patient disposition will be for all screened patients.

4.2. Demographics and Baseline Characteristics

Demographics and baseline characteristics will be summarized and presented by subgroup of RGDO and overall. Age at enrollment, height at baseline, weight at baseline, waist circumference at baseline, and BMI at baseline will be summarized using descriptive statistics (N, mean, SD, 90% CI of the mean, median, minimum, and maximum). The number and percentage of patients in each sex, ethnicity, race, baseline Fitzpatrick classification, and genetic deficiency categories will be presented. The number and percentage of patients with cognitive impairment will also be presented. No formal statistical comparisons will be performed. Patient demographics will include patients in the FAS.

4.3. All Medical History events will be coded using the MedDRA coding system and displayed in tables by RGDO and overall, and in data listings using system organ class and preferred term. Efficacy Analyses

4.3.1. Primary Analysis

The primary analysis on the primary endpoint will be based on the FAS.

The primary endpoint is the proportion of patients in each subgroup of RGDO who achieve at least 5% reduction from baseline in body weight (i.e., are 'responders') after ~3 months of treatment with setmelanotide.

The visit designated for analysis at ~3 months of treatment will be identified as follows: A patient's therapeutic dose will first be established. For patients enrolled prior to amendment 9, therapeutic dose will be considered the max dose received during the dose escalation phase (identified by Clinical Visit 2X). For patients enrolled post-amendment 9, the therapeutic dose will be considered the dose received at Visit 3. The first date that this dose was received will be considered the date of the first therapeutic dose (this will be the date of Visit 3 for post-amendment 9 patients). If a patient has a visit falling within 60 to 120 days after first therapeutic dose, this visit should be considered for analysis as ~3 months of treatment. If a patient has two visits falling within this window, the visit closest to Day 90 should be considered. If a patient has two visits falling within this window that are equidistant from Day 90, the later visit should be considered. If a patient has no visit falling within this window, the last observation before the window will be used for analysis purposes. If a patient has no visit falling within this window and no observation prior to the window, this patient will be treated as missing for analysis purposes.

The summary of the primary endpoint and the associated two-sided 90% Clopper-Pearson

confidence interval will be provided. Descriptive statistics for the actual, change, and percent change from baseline in body weight (kg) at the ~3 month analysis endpoint will be presented for patients of the FAS by RGDO.

Body weight (kg) will be recorded as shown in the SOA ([Table 1-1](#), [Table 1-2](#), [Table 1-3](#), and [Table 2](#)). Weight is repeated in triplicate and the mean weight is calculated per study visit. Mean weight will be utilized for analysis purposes.

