Eligible patients will return to the clinic within 2 – 8 weeks of completing the Screening Visit for the Baseline Visit (Visit 2) and first dose of setmelanotide. Dose levels for all patients will escalate to a final dose of 3.0 mg/day during an initial dose-titration phase, but the starting dose will depend on patient age. Patients 6 up to 16 years old will initially be dosed at 1.0 mg/day for 2 weeks, beginning at the Baseline Visit on Study Day 1. Starting on Day 15, the dose will escalate to 2.0 mg/day and remain at that level for 2 weeks, until the patient returns to clinic for Visit 3 on Day 29. At Visit 3, the dose will be escalated to 3.0 mg/day; the patient will continue dosing at 3.0 mg/day for 12 weeks. Patients ≥16 years old will initiate dosing at 2.0 mg/day at the Baseline Visit, and continue dosing at that level for 2 weeks. The dose will be escalated to 3.0 mg/day beginning on Study Day 15, and the patient will continue that dose for 14 weeks. Study site staff will call all patients at their homes after the first 2 weeks of treatment to ensure the escalation occurred as planned and collect any adverse events (AEs).

Patients will continue dosing at 3.0 mg/day and return to the clinic every four weeks (Visits 3-5) to complete the assessments in [Table 2](#). After 16 weeks in the study, patients will return to the clinic for Visit 6. At Visit 6, the patient will receive the last setmelanotide injection.

Participation in the study will then conclude in one of the following two ways:

- Complete Visit 6 and enroll in a separate extension study, Rhythm Study RM-493-022. If RM-493-022 is not yet open at the clinic site, the patient will continue daily setmelanotide injections and other activities per the current study, as presented in the Schedule of Assessments (SOA) ([Table 2](#)). The patient will return to the clinic for Bridging Visits every 12 weeks for up to one year, until the extension study opens at the site. Additional clinic visits may be scheduled at the discretion of the primary investigator (PI).
- Decide not to participate in the extension study and proceed to the final study visit (Visit 7) in 4 weeks.

Patients on study prior to amendment 9 should transition to dose escalation as outlined in protocol amendment 9 in the manner outlined below:

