2. ANALYSIS POPULATION

2.1. Population Definitions

The following analysis populations will be evaluated and used for presentation and analysis of the data:

- Safety Analysis (SA) Set: All patients who received at least 1 dose of study drug, excluding patients from Axis Sites #22 through #27 inclusive.
- Full Analysis Set (FAS): All patients who received at least 1 dose of study drug and have baseline weight data, excluding patients from Axis Sites #22 through #27 inclusive.
- Completer's Set (CS): All patients in the FAS who have non-missing weight data collected at least once between 60 days and 120 days on therapeutic dose, inclusive.
 - For patients enrolled prior to amendment 9, therapeutic dose will be considered the maximum dose received during the dose escalation phase (identified by Clinical Visit 2X). For patients enrolled post-amendment 9, the therapeutic dose will be considered the dose received at Visit 3.
 - The first date that this dose was received will be considered the date of the first therapeutic dose (this will be the date of Visit 3 for post-amendment 9 patients). If a patient has a visit falling within 60 to 120 days after first therapeutic dose and was still on treatment, this visit should be considered for analysis as ~3 months of treatment. If a patient has two visits falling within this window, the visit closest to Day 90 in which the patient was still on treatment should be considered. If a patient has two visits falling within this window that are equidistant from Day 90, the later visit should be considered. For post-amendment 9 patients, if the patient's last visit during the study is Study Visit 5 and the patient is still on treatment, then that date should be used for this analysis, even if it does not fall within 60 to 120 days after first therapeutic dose. If a patient has no visit falling within this window, this patient will be treated as missing for completer's analysis purposes. If a patient has no visit falling within this window and no observation prior to the window, this patient will be treated as missing for analysis purposes, as well.
- Per-Protocol (PP) Set: All patients in the FAS without any major protocol violations.

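### SAP 4.3.1: the primary visit rule can classify a post-Amendment 9 patient with no Visit 6 weight on the planned off-drug Visit 7, and it defines the anchor date in two ways

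*SAP*

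**What the plan says.** The primary endpoint is at least 5% weight reduction after about 3 months of treatment, analysed in the FAS. SAP 4.3.1 picks the visit: "If a patient has a visit falling within 60 to 120 days after first therapeutic dose, this visit should be considered for analysis". If two visits qualify, the one nearer Day 90 is taken. If they are "equidistant from Day 90, the later visit should be considered". If none qualifies, "the last observation before the window will be used for analysis purposes".

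The Completer's Set rule in SAP 2.1 uses the same window in almost the same text, with a condition added; its wording there runs: "first therapeutic dose and was still on treatment, this visit should be considered for analysis as ~3 months of treatment". SAP 2.1 repeats that condition for choosing between two visits. SAP 4.3.1 has it in neither place.

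Both sections take the dose received at Visit 3 as the therapeutic dose for post-Amendment 9 patients. They anchor the window on the first date that dose was received, then add in parentheses that "this will be the date of Visit 3 for post-amendment 9 patients".

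On dosing, SAP 1.3.1 says for patients 16 and over: "The dose will be escalated to 3.0 mg/day beginning on Study Day 15, and the patient will continue that dose for 14 weeks". Patients under 16 first receive 3.0 mg at Visit 3 (SAP Table 2, footnote 29). On the end of treatment: "At Visit 6, the patient will receive the last setmelanotide injection". Patients who do not enter the extension "Decide not to participate in the extension study and proceed to the final study visit (Visit 7) in 4 weeks". SAP Table 2 schedules a weight at Visit 7, and its footnote 30 places the endpoint analysis at Visit 6.

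**The concern.** The endpoint describes response on treatment. Visit 7 is by design a post-treatment visit, yet nothing in the primary rule keeps it from being chosen, and the window is wide enough to include it. When the Visit 6 weight is missing, one would expect the last on-drug weight to stand in. The fallback to an earlier observation applies only if no visit lies in the window, so Visit 7 blocks it.

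The anchor is a second ambiguity in the same rule. The definition and the parenthesis give different dates for patients 16 and over. Two programmers could each follow the SAP and select different visits.

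The selected visit also feeds the descriptive weight change at about 3 months (SAP 4.3.1) and the 3-month hunger summary (SAP 4.3.2). Subgroups are expected to hold 1 to 15 patients (Protocol 8.1), so one classification is visible in the estimate. The results are meant to inform whether further development in a population is appropriate (Protocol 7.3).

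**Working it through.** **Inputs.** SAP Table 2 study days, each ±3: Visit 3 = 29, Visit 4 = 57, Visit 5 = 85, Visit 6 = 113, Visit 7 = 141. The home dose escalation is on Day 15. Window 60 to 120 days, target Day 90, ties to the later visit (SAP 4.3.1).

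**The plan's own figures.** Time at 3.0 mg up to Visit 6 is (113 − 29)/7 = 12 weeks under 16 and (113 − 15)/7 = 14 weeks at 16 and over. Both match SAP 1.3.1.

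**Days since anchor** (visit day minus anchor day):

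| Anchor | Visit 5 | Visit 6 | Visit 7 |
|---|---|---|---|
| Visit 3 (Day 29) | 56 | 84 | 112 |
| Day 15 (definition, 16 and over, planned dosing) | 70 | 98 | 126 |
| Day 1 (definition, starting dose still given at Visit 3) | 84 | 112 | 140 |

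**Visit 6 weight missing, Visit 7 attended.** All 7 × 7 × 7 = 343 combinations of ±3 days on the anchor, Visit 5 and Visit 7 were run.
- Visit 3 anchor: Visit 7 (106 to 118 days) is selected in 343 of 343. Visit 5 (50 to 62 days) is sometimes inside the window, but then it is 28 to 30 days from Day 90. Visit 7 is at most 28 days away and wins ties. If the anchor date itself counts as Day 1, Visit 7 is selected in 340 of 343.
- Day 15 anchor: Visit 5 is selected in 343 of 343.
- Visit 7 barred: Visit 5 is selected in every combination under both anchors, either inside the window or as the last observation before it.

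For patients under 16 on planned dosing, definition and parenthesis agree on Day 29, so the problem exists under either reading. For patients 16 and over it follows only from the parenthesis.

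**Visit 6 weight present, planned dosing.** All 7⁴ = 2,401 combinations were run. With the Visit 3 anchor, Visit 6 is selected in 2,401 of 2,401 under either day count. With the Day 15 anchor it is 2,401 in elapsed days, but 2,380 if the anchor date is Day 1 (Visit 5 in the other 21). The day count therefore needs stating.

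**Dose deviated from plan** (Protocol 9.2 allows this). For a patient still on the starting dose at Visit 3, the definition gives Day 1, which is 29 − 1 = 28 days before Visit 3. Visit 5 is then 6 days from Day 90 and Visit 6 is 22 days away. With Visits 5 and 6 both available and each ±3, Visit 5 is selected in 49 of 49. The Visit 3 anchor selects Visit 6 in 343 of 343.

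**Size, as illustration.** One changed classification moves the rate by 1/5 = 20 points or 1/15 = 6.7 points. In the SAP's two-sided 90% Clopper-Pearson interval:
- cohort of 5: 3/5 gives 18.9–92.4%, and 2/5 gives 7.6–81.1%;
- cohort of 15: 8/15 gives 30.0–75.6%, and 7/15 gives 24.4–70.0%.

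**The case against.** **The difference may be deliberate.** An inclusive FAS beside a restricted Completer's Set is a recognised arrangement, and Protocol 13.4 keeps all collected data in the analyses. That is possible, but the SAP does not say so, and keeping all data does not settle which visit represents about 3 months of treatment. The Completer's Set analysis is optional (SAP 2.1). On schedule it does not repair the classification either. This patient's Visit 5 is outside the window, and the Visit 5 exception needs Visit 5 to be the last visit, so the patient counts as missing there.

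**The case is narrow.** This stands. The patient must decline the extension, lack a Visit 6 weight, have no unscheduled or additional visit to substitute under SAP 3.11, and attend Visit 7. The four-week gap off drug is also firm only if Visit 6 was attended. If it was missed, the documents do not say when dosing ended.

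**The anchor is already operational.** The parenthesis does give a usable date, and keeping it is an acceptable solution. It still contradicts the definition beside it.

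**Stronger readings the documents do not support.**
- A reader might infer that the rule lowers the responder rate. Selecting Visit 7 does not by itself change a classification. Visit 7 also follows further planned dosing after Visit 5, so the net change between them could go either way.
- A reader might infer that development decisions turn on this. Protocol 7.3 says only that the study provides data towards them, and SAP 3.1 makes the analysis descriptive.
- A reader might extend the point to pre-Amendment 9 patients. SAP 3.11 leaves the mapping of visits, for those not moved to the new schedule, to a separate document that was not provided. No claim is made for them.

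**Conclusion.** The point holds for post-Amendment 9 patients, within limits. As written, the primary rule classifies a patient with no Visit 6 weight and no substitute visit on the planned off-drug Visit 7 while an on-drug Visit 5 weight exists. That conflicts with the endpoint's wording and with footnote 30. It assumes that a visit needs a recorded weight to be selected. Patients with an on-schedule Visit 6 weight, planned dosing and the Visit 3 anchor are unaffected.

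The anchor contradiction is a separate, real inconsistency. It amounts to 14 days for patients 16 and over on planned dosing. For a patient of any age still on the starting dose at Visit 3 it is 28 days, and the definition then passes over an available Visit 6 weight.

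The effect on the estimate is conditional. It is 20 points in a cohort of 5, or 6.7 in a cohort of 15, per patient whose Visit 5 and Visit 7 weights straddle the 5% threshold. How often that happens cannot be derived from the documents. The wording should be corrected, but this does not show that the planned results are biased.

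**What to change.** 1. In SAP 4.3.1, state that planned post-treatment visits (Visit 7 and any equivalent off-drug visit) cannot be selected as the 3-month visit, so that the last on-treatment weight is used.
2. In SAP 4.3.1 and 2.1, reconcile the anchor definition with the parenthesis and with the dosing passages. Two wordings would do: use the Visit 3 date for all post-Amendment 9 patients, or give an on-treatment Visit 6 weight explicit priority. Anchoring only on the first date of the Visit 3 dose would not, because it can pass over Visit 6 when the dose deviated.
3. State whether days are elapsed days or count the anchor date as Day 1.
4. Also report the primary result with Visit 7 allowed. Restricting to on-treatment weights may slightly raise the responder rate in an uncontrolled trial, so the choice should be visible.

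The cost is a few sentences of SAP text, a small programming change using visit labels and the last-dose date, and one extra summary. No new data are needed.

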- 6 The Dose Titration phase will be a variable schedule lasting a minimum of 2 weeks in which patients will return to the clinic approximately every 2 weeks in order to establish the individual patient's therapeutic dose according to Protocol. Given the variable number of dose titration steps in the Dose Titration Phase, each Dose Titration Visit Number (V) will remain V2 with an alphabetized suffix added to each titration visit (i.e.; first dose titration at start of Week 1 = V2a, second dose titration at start of Week 3 = V2b, etc.). This will allow for the Visits to be appropriately tracked. Additionally, each dose titration visit will have the same pre and post dose assessments as outlined in the SOA (with the exception of Anti-Rm-493 antibodies, metabolic and hormonal assays, ECG, Inclusion/Exclusion review and Medical History Review).
- 7 Once the patient's individual therapeutic dose is established the patient will enter the Open Label Active Treatment phase for 10 additional weeks, for a combined total of 12 weeks of dosing at the therapeutic dose. During this time, the study calendar will be reset, starting when the therapeutic dose was initiated (i.e. the last 2 weeks of dose titration when the therapeutic dose was established). Therefore, the Open Label Active Treatment phase starts at the beginning of Week 3 (V2x – final dose titration visit). Patients losing 5 kg of weight (or 5% if baseline weight is < 100 kg) at the end of the Open Label Treatment phase will be eligible to enter the one-year extension.
- 8 During the titration period and the 10-week Open Label Treatment Period, patients (and/or parents/guardians) will measure blood pressure and heart rate at home once daily prior to dosing in the morning, and record the values. The measurements should be taken in triplicate and all 3 readings recorded. If needed, Rhythm will supply a blood pressure machine for these readings.

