The FAS is the primary population for the analysis of efficacy parameters. Sensitivity analyses of efficacy parameters may be conducted on the CS population, if appropriate. A subset of efficacy parameters may be evaluated for the PP Set if the population in PP is over 20% different from the FAS population. The SA Set is the primary population for the analysis of PK parameters and safety endpoints.

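### SAP 4.3.1 carries forward the last pre-window weight with no on-treatment condition, so a patient who stopped drug by about Visit 4 can be reported as a ~3-month responder

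*SAP*

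**What the plan says.** SAP 4.3.1 bases the primary analysis on the FAS, defined in SAP 2.1 as "All patients who received at least 1 dose of study drug and have baseline weight data" (certain sites excluded). The analysed weight is the one from a visit 60 to 120 days after the first therapeutic dose; of two such visits, the one closer to Day 90 is taken. Failing that: "If a patient has no visit falling within this window, the last observation before the window will be used for analysis purposes". A patient with no visit in the window and "no observation prior to the window, this patient will be treated as missing for analysis purposes".

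The clock starts on the first date the therapeutic dose was received. For patients enrolled after amendment 9 a parenthesis says "this will be the date of Visit 3 for post-amendment 9 patients". For earlier patients, a footnote to the schedule in SAP 1.3.4 says "the study calendar will be reset, starting when the therapeutic dose was initiated".

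The Completer's Set in SAP 2.1 uses the same window but adds a treatment condition: the visit must fall 60 to 120 "days after first therapeutic dose and was still on treatment, this visit should be considered for analysis as ~3 months of treatment". It makes one exception, for a post-amendment 9 patient whose "last visit during the study is Study Visit 5 and the patient is still on treatment". A patient with no visit in the window is otherwise missing from that analysis. Its status is optional: "Sensitivity analyses of efficacy parameters may be conducted on the CS population, if appropriate".

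**The concern.** The endpoint is worded as response after about 3 months of treatment, but the derivation lets a shorter exposure stand in for it. A patient who loses 5% early, stops drug and is not weighed in the window is scored as a success on a weight taken weeks before the window opens. The Completer's Set text shows that treatment status was considered for the same window. It does not fill the gap, because it is optional and leaves these patients out instead of counting them.

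The trial has no control arm, Protocol 8.1 expects 1 to 15 patients per subgroup, and Protocol 7.3 says the data will inform whether further development is appropriate. With no formal test, the subgroup proportion is itself the result, and one patient's classification is visible in it.

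**Working it through.** **1. Visits on the SAP clock.** Study days come from SAP Table 2: Visit 3 = 29, Visit 4 = 57, Visit 5 = 85, Visit 6 = 113, Visit 7 = 141, each ±3 days. Patients aged 16 or over first receive 3.0 mg on Day 15 (SAP 1.3.1; Protocol Table 2). Days after anchor = visit day − anchor day.

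| Visit | Anchor Visit 3 (Day 29) | Anchor Day 15 (age ≥16) |
|---|---|---|
| 4 | 57 − 29 = 28 | 57 − 15 = 42 |
| 5 | 85 − 29 = 56 | 85 − 15 = 70 |
| 6 | 113 − 29 = 84 | 113 − 15 = 98 |
| 7 | 141 − 29 = 112 | 141 − 15 = 126 |

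Allowing ±3 days at both ends, Visit 4 lies at 22–34 or 36–48 days, so it precedes day 60 on either anchor. The gap to the window is 60 − 28 = 32 days or 60 − 42 = 18 days. Time since first dose at Visit 4 is 57 − 1 = 56 days (8 weeks).

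The pre-amendment 9 reset calendar (SAP Table 1-2) puts Visits 4, 5 and 6 on Days 29, 57 and 85, that is 28, 56 and 84 days after the start. Time since first dose varies with titration.

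**2. Applying the rule to a patient who stops at Visit 4 with at least 5% loss.**
- No later weight: Visit 4 is carried forward and the patient is a responder.
- Off-drug weight 4 weeks later (Day 57 + 28 = 85): on the Visit 3 clock this is day 56, before the window, so it is the weight carried forward. On the Day 15 clock it is day 70, inside the window, and is used directly. If it still shows 5% loss, the patient is a responder on either clock.
- Off-drug weight inside the window on either clock: used as it stands.

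**3. Size per patient.** The shift is 100/n: 100/5 = 20, 100/10 = 10, 100/15 = 6.7 points. The two-sided 90% Clopper-Pearson limits are the 0.05 quantile of Beta(x, n − x + 1) and the 0.95 quantile of Beta(x + 1, n − x). Illustrative counts:

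| n | Stopper counted as responder | Stopper counted as non-responder |
|---|---|---|
| 5 | 3/5 = 60% (18.9–92.4) | 2/5 = 40% (7.6–81.1) |
| 10 | 5/10 = 50% (22.2–77.8) | 4/10 = 40% (15.0–69.6) |
| 15 | 6/15 = 40% (19.1–64.0) | 5/15 = 33.3% (14.2–57.7) |

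**4. Expected size, by assumption only.** Let d be the share of patients who stop before the ~3-month assessment and q the share of those whom 4.3.1 scores as responders. The documents give neither. Taking d = 5–20% and q = 0–50%, the mean gap d × q runs from 0.05 × 0 = 0 to 0.20 × 0.50 = 10 points. Assuming independent patients, the chance of at least one such patient in a subgroup is 1 − (1 − dq)^n:

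| dq | n = 5 | n = 10 | n = 15 |
|---|---|---|---|
| 0 (q = 0) | 0% | 0% | 0% |
| 0.025 (d = 10%, q = 25%) | 11.9% | 22.4% | 31.6% |
| 0.10 (both maxima) | 41.0% | 65.1% | 79.4% |

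**5. Denominator.** Take five FAS patients, two responders and one patient with no post-baseline weight. Depending on whether the missing patient stays in the denominator, the rate is 2/5 = 40% (7.6–81.1) or 2/4 = 50% (9.8–90.2). SAP 4.3.1 does not say which.

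**The case against.** The carry-forward is a disclosed choice. Protocol 13.4 leaves missing data to the SAP, asks that all collected data be used, and calls every p-value and interval exploratory; SAP 3.1 and 3.7 treat the results as descriptive. No go/no-go rate is stated. By-patient listings and weight summaries at every visit would expose any such case in a subgroup this small.

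The route is also limited. A discontinuation weight is scheduled, and the pre-amendment 9 footnotes allow home assessments or telephone contact to collect weight. A patient whose last on-treatment weight is at Visit 5 has had 85 − 1 = 84 days of drug, which is arguably 3 months. The sections between SAP 4.3.2 and 4.6 are redacted and may hold another analysis. All of this stands. It limits the harm, but it does not supply the missing condition or a pre-specified alternative.

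Some stronger readings are tempting but not supported:
- **That the rule inflates the rate in general.** It cannot give a lower rate than non-responder imputation. Against leaving early stoppers out, it can move the rate either way, because stoppers with less than 5% loss count as failures.
- **That Visit 4 is always 32 days short of the window.** That holds on the Visit 3 anchor only.
- **That it is open whether baseline counts as an earlier observation.** The text largely settles this. Every FAS patient has a baseline weight, so counting it would leave the missing category empty.

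**Conclusion.** The concern holds as a statement of what the rule permits. A patient who stopped drug around Visit 4 or earlier, with at least 5% loss at the last pre-window weight and no weight in the window, is reported as a ~3-month responder. An off-drug weight in the window is accepted as well. This is true on both anchor readings, which disagree for patients aged 16 or over and need reconciling.

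The firm figure is 20, 10 or 6.7 points per patient at n = 5, 10 or 15, with widely overlapping intervals. How often it would happen rests on assumed values of d and q, and the range starts at zero. A reader might infer a false-positive finding or a known upward bias. The documents support neither: no formal hypothesis is tested and no dropout rate is given. The harm is a descriptive proportion that may be optimistic relative to counting early stopping as failure, with no visible pre-specified analysis to show by how much. This is worth changing because the remedy is cheap.

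**What to change.** Keep the 4.3.1 rule as primary. Beside it, pre-specify for each subgroup a responder analysis on the full FAS denominator, with its two-sided 90% Clopper-Pearson interval:

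- **(a)** Non-responder: a patient who stopped drug before the analysed ~3-month visit, who stopped before Visit 3 (post-amendment 9), or who has no post-baseline weight. This applies whether or not an off-drug weight falls in the window.
- **(b)** Used as observed: an on-treatment weight in the window, or an on-treatment Visit 5 weight where that is the last visit, as SAP 2.1 already allows. The Visit 5 case takes precedence over (a).
- **(c)** Current carry-forward: a patient still on drug with no weight in the window.

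Define stopping for (a) so that a patient who finishes treatment as scheduled at Visit 6 is not caught by it.

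In the same edit, reconcile the two anchor statements, state the primary denominator for patients treated as missing, and say how a patient with no Visit 3 is handled.

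The cost is SAP wording and one derivation from weights already collected; on-treatment status is already needed for the Completer's Set. The downside is a second rate per subgroup, equal to or less favourable than the primary.

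### SAP 4.3.1 does not fix the denominator of the primary responder proportion for patients without a usable weight, and gives no analysis window to post-Amendment 9 patients who stop before Visit 3

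*SAP*

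**What the plan says.** **Analysis set.** SAP 4.3.1 states: "The primary analysis on the primary endpoint will be based on the FAS". SAP 2.1 defines that set as "All patients who received at least 1 dose of study drug and have baseline weight data", apart from a list of excluded sites. No post-baseline weight is required.

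**Choosing the ~3-month weight.** SAP 4.3.1 takes the visit 60 to 120 days after the first therapeutic dose, and the one closest to Day 90 if there are two. With no such visit, "the last observation before the window will be used for analysis purposes". With no in-window visit and "no observation prior to the window, this patient will be treated as missing for analysis purposes".

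**Anchor.** For post-Amendment 9 patients "the therapeutic dose will be considered the dose received at Visit 3". The date of first therapeutic dose is fixed in the same way: "this will be the date of Visit 3 for post-amendment 9 patients". No alternative is given for a patient who has no Visit 3.

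**Other text on missing data.** Protocol 13.4 leaves missing data to the SAP. SAP 3.10 says that, in general, nothing is substituted for missing values. It does not mention denominators.

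**The concern.** The rule for the primary endpoint leaves two things open.

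1. **Denominator.** Two readings have support in the text.
   - *Exclusion.* SAP 2.1 uses nearly the same phrase, "this patient will be treated as missing for completer's analysis purposes", for patients with no in-window visit, who in general fall outside the Completer's Set. SAP 3.10 argues against filling in a value.
   - *Full denominator.* The analysis is stated to be on the FAS, and the endpoint counts those who reach the 5% loss. A patient with no weight has not been shown to reach it.

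   Whether baseline is an observation before the window is also unstated, and that decides whether the missing category can contain anyone.

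2. **Anchor.** A post-Amendment 9 patient who stops before Visit 3 received no Visit 3 dose. Such a patient therefore has no window and no period before it. SAP Table 2 schedules a weight at the Treatment Discontinuation Visit, but the carry-forward rule cannot place that weight.

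The result at stake is the headline percentage and its 90% interval in cohorts expected to hold 1 to 15 patients (Protocol 8.1). Two programmers could each follow 4.3.1 faithfully and report different figures.

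**Working it through.** **Inputs from the documents.** Cohort size is at least 5 (SAP 3.1) and expected to be 1 to 15 (Protocol 8.1). The interval is two-sided 90% Clopper-Pearson (SAP 4.3.1). The post-Amendment 9 visits are planned for Days 1, 29, 57, 85, 113 and 141 (SAP Table 2).

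**Assumed inputs.** The documents give no responder rate, dropout rate or power, so there is no plan figure to reproduce. I assume 40% responders, with a range of 20% to 60%, and m=1 patient without a usable weight.

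**Formula.** With r responders among n FAS patients, of whom m are missing:

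- missing counted as non-responder: r/n
- missing dropped: r/(n-m) = (r/n) × n/(n-m)
- difference: (r/n) × m/(n-m), which is never negative

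| n | r | Dropped, r/(n-1) (90% CI) | Full FAS, r/n (90% CI) | Difference (points) |
|---|---|---|---|---|
| 3 | 1 | 1/2 = 50.0% (2.5 to 97.5) | 1/3 = 33.3% (1.7 to 86.5) | 16.7 |
| 5 | 2 | 2/4 = 50.0% (9.8 to 90.2) | 2/5 = 40.0% (7.6 to 81.1) | 10.0 |
| 10 | 4 | 4/9 = 44.4% (16.9 to 74.9) | 4/10 = 40.0% (15.0 to 69.6) | 4.4 |
| 15 | 6 | 6/14 = 42.9% (20.6 to 67.5) | 6/15 = 40.0% (19.1 to 64.0) | 2.9 |

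Over 20% to 60% responders with m=1, the difference is 5.0 to 15.0 points at n=5, 2.2 to 6.7 at n=10 and 1.4 to 4.3 at n=15.

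**When the difference is zero.** It is zero if nobody responds (r=0) or if every patient has a usable post-baseline weight (m=0). It is also zero if baseline is carried forward as 0% change, because the patient is then a non-responder in the full denominator.

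**Who could be affected.** On the post-Amendment 9 schedule no weight falls between Day 1 and Day 29, since the Day 15 contact is a telephone call. A patient who stops in that interval and misses the Treatment Discontinuation Visit has no scheduled post-baseline weight. Protocol 12.2.4 only encourages a final visit after withdrawal for an adverse event. Pre-Amendment 9 patients were weighed about every two weeks during titration, so only very early losses count there.

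**Window positions, planned days:**

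| Anchor | Window (study days) | Visit 5 | Visit 6 | Visit 7 |
|---|---|---|---|---|
| Visit 3, Day 29 | 29+60=89 to 29+120=149 | 85-29=56, out | 113-29=84, in | 141-29=112, in |
| Day 15 | 15+60=75 to 15+120=135 | 85-15=70, in | 113-15=98, in | 141-15=126, out |

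Day 15 is when patients aged 16 or older are first scheduled to receive 3.0 mg, the dose planned at their Visit 3. When a Visit 6 weight exists, both anchors select it on the planned schedule (6 and 8 days from Day 90). When it is absent, the Visit 3 anchor selects Visit 7, four weeks after the planned last dose, and the Day 15 anchor selects Visit 5.

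**The case against.** The strongest reply is that the missing category is empty. Every FAS patient has a baseline weight, and SAP 3.4 takes baseline before the first dose, so read literally it is an observation before the window. It is then carried forward and the patient is a non-responder. This stands as a possible reading, and under it the denominator effect is nil. It leaves the sentence on missing patients with nothing to do, however, and for a patient without Visit 3 there is no window for baseline to precede. The SAP does not say that this reading is meant.

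Three further replies limit the point:

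- Exposure is narrow, as shown in the working.
- No formal hypothesis is tested (Protocol 13.2), and SAP 3.1 presents intervals as estimation only. In every row of the table the two intervals overlap heavily.
- By-patient listings, and the N beside the ~3-month weight summaries, would let a reader see who is missing. They do not define the headline proportion. The Completer's Set does not settle it either: its analysis is optional, and it generally drops these same patients.

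Two stronger inferences go too far. A reader might infer that the plan removes early stoppers and so inflates the rate. Exclusion is a natural reading of the wording, but the text does not commit to it. A reader might also infer that 4.3.1 is in error because SAP 2.1 asks for a visit "within 60 to 120 days after first therapeutic dose and was still on treatment" and 4.3.1 does not. That condition sits in the Completer's Set definition, and a looser rule for the FAS may be deliberate. Protocol 13.4's retention of data outside visit windows does not settle this: it most naturally concerns scheduled visit windows, not the 60 to 120 day analysis window.

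**Conclusion.** The point holds as a minor gap in the definition of the primary estimate. SAP 4.3.1 leaves open whether baseline counts as an earlier observation, whether a patient treated as missing stays in the denominator, and what applies without a Visit 3.

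If missing is applied as exclusion, the bias has one direction: the proportion rises or is unchanged. With one such patient and an assumed 40% responders, the shift is 10.0 points at n=5 and 2.9 points at n=15. These figures require that an observation means a post-baseline weight and that missing means dropped. The anchor gap is established from the text but not quantified, because the documents do not say how many patients stop before Visit 3.

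No test and no stated responder-rate threshold depends on the result. The effect is confined to the reported percentage and interval, and is largest in the smallest cohorts.

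**What to change.** In SAP 4.3.1, state that:

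- (a) the denominator is every FAS patient in the cohort;
- (b) baseline is not an observation prior to the window, and a patient with no post-baseline weight is a non-responder;
- (c) a post-Amendment 9 patient with no Visit 3 stays in the denominator and is classified by the last available post-baseline weight, including the Treatment Discontinuation Visit, or otherwise as a non-responder.

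Report for each cohort how many weights are in-window, carried forward or absent, and cross-refer SAP 3.10 to this rule.

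**Optional.** State whether the on-treatment condition of SAP 2.1 is meant to apply in 4.3.1, and give the result both ways. The choice should be worded consistently with (c), which can admit a weight taken after the drug was stopped. Also reconcile the first date the dose was received (planned Day 15 for patients aged 16 or older) with the Visit 3 date (Day 29) given in parentheses.

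**Cost.** A few sentences, one cross-reference and one set of counts per cohort, with no new data. The downside is that responder percentages may be lower than under exclusion, by 1.4 to 15.0 points for one missing patient over n=5 to 15 and 20% to 60% responders.
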